3.5. Study end-points

3.5.1. Primary study end-point acetazolamide arm

Total urinary sodium excretion (mmol) after 24 h

3.5.2. Primary study end-point for spironolactone arm

Incidence of hypo- (serum potassium <3.5mmol/L or need for oral/intravenous potassium supplements) or hyperkalemia (serum potassium >5.0mmol/L) during the entire 72 h interval after randomization.

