MRA have an established role in the treatment of chronic CHF.^{11, 12} However there are remarkable few data on their use in patients who present with ADHF. Nevertheless, in this context with frequent use of potassium wasting diuretics, they might be of particular interest to prevent occurrence of hypokalemia, which has been associated with a worse prognosis.²⁷ Moreover, by inhibiting distal tubular sodium reabsorption and counteracting aldosterone breakthrough, MRA might improve the natriuretic efficiency of loop diuretics.

2. Study Hypotheses

1. Combination therapy with acetazolamide improves loop diuretic efficacy to induce natriuresis in ADHF patients, allowing for a lower dose of the latter medication and potentially less adverse events such as worsening renal function.
2. Combination therapy with acetazolamide and low-dose loop diuretics leads to less pronounced neurohumoral activation compared to treatment with high-dose loop diuretics in ADHF patients.
3. Upfront therapy with MRA is safe in patients presenting with ADHF and lowers the incidence of hypokalemia and the need for potassium supplementation, without causing a higher incidence of hyperkalemia.
4. Combination diuretic therapy with acetazolamide and/or upfront spironolactone will lead to improved clinical outcome (less heart failure rehospitalizations and lower all-cause mortality).

3. Study Protocol

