3.2. Study population

3.2.1. Inclusion criteria

- Older than 18 years of age and able to give informed consent
- Clinical diagnosis of ADHF within the previous 8 h
- At least two clinical signs of congestion (e.g. edema, ascites, jugular venous distension or pulmonary vascular congestion on chest radiography)
- Maintenance therapy with oral loop diuretics at a dose of at least 1 mg bumetanide or an equivalent dose for at least 1 month before hospital admission
Conversion: 1 mg bumetanide = 40 mg furosemide = 20 mg torsemide
- Plasma NT-proBNP >1,000 pg/mL
- Left ventricular ejection fraction <50% (on examination ≤3 months)
- One out of three of the following criteria:
 - Serum sodium <136 meq/L

- Urea/creatinine ratio >50
- WRF defined as a >0.3 mg/dL increase in Cr compared to a previous value within 3 months before admission

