3.3.4. Arm 2, treatment group: Upfront spironolactone

This group will receive oral spironolactone 25 mg immediately after randomization and subsequently each day in the morning (10u00) provided serum potassium levels are <5.0 mmol/L. If no contraindications emerge during hospitalization, spironolactone will be added to the maintenance therapy of the patient upon hospital discharge.

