3.4. Collected data

- Baseline at the moment of randomization
 - Demographics, medical history, current medical therapy, baseline body weight, blood pressure, heart rhythm (sinus or not), heart rate, Visual-analogue scale (VAS) score for dyspnea and 4-point Likert scale for edema will be assessed upon study inclusion
 - Blood sample: hematocrit, electrolytes, serum osmolality, serum urea, serum creatinine, serum Cystatin C, serum urate, plasma renin activity (PRA), plasma aldosterone, plasma adrenaline, plasma noradrenaline, total protein, plasma NT-proBNP
- Day 1-3:
 - VAS score for dyspnea
 - 4-point Likert scale for edema
 - Body weight and fluid balance
 - Blood pressure, heart rate, heart rhythm
 - Blood sample: hematocrit, electrolytes, serum osmolality, serum urea, serum creatinine, serum Cystatin C, serum urate, PRA, plasma aldosterone, plasma adrenaline, plasma noradrenaline, total protein, plasma NT-proBNP
- Three consecutive 24h urinary collections will be performed; the first one started with the first bolus administration of loop diuretics; urinary assessment of creatinine, protein, sodium, potassium, chloride, ureum, urate, microalbuminuria
- At an outpatient follow-up appointment 2-6 weeks after hospital discharge, a final blood sample with hematocrit, electrolytes, serum osmolality serum urea, serum creatinine, serum Cystatin C, serum urate and plasma NT-proBNP will be collected.
- All-cause mortality and hospital readmissions will be collected prospectively for the study cohort. The patient will receive a telephone call from a study nurse after 3, 6, 9 and 12 months

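### The Arm 2 primary end-point is called an incidence but is not anchored to baseline, so continuing supplements or a persisting entry abnormality can count as events and dilute the spironolactone contrast

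*Combined protocol and SAP*

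**What the plan says.** Section 3.5.2 gives the Arm 2 primary end-point as "Incidence of hypo- (serum potassium <3.5mmol/L or need for oral/intravenous potassium supplements"), "or hyperkalemia (serum potassium >5.0mmol/L) during the entire 72 h interval after randomization". All three components are absolute states. None requires a normal baseline value, a change from baseline, or a supplement started after randomization.

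Hypothesis 3 in section 2 states the claim under test, that upfront MRA therapy "lowers the incidence of hypokalemia and the need for potassium supplementation, without causing a higher incidence of hyperkalemia".

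Neither eligibility list has a criterion for serum potassium or for potassium supplements. Section 3.2.1 requires "Maintenance therapy with oral loop diuretics at a dose of at least 1 mg bumetanide or an equivalent dose for at least 1 month" before admission. Section 3.2.2 excludes on eGFR only below 15 mL/min/1.73m². Section 3.3.4 gives upfront spironolactone "provided serum potassium levels are <5.0 mmol/L".

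Section 3.4 collects the relevant baseline data: "Blood sample: hematocrit, electrolytes, serum osmolality, serum urea, serum creatinine" at randomization, and "Demographics, medical history, current medical therapy, baseline body weight" among the clinical items. Neither 3.5.2 nor the statistical section (3.6) uses them for this end-point. By contrast, section 3.5.3 defines worsening renal function and persistent renal impairment relative to baseline.

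**The concern.** All patients arrive on a loop diuretic, and section 1 itself links potassium-wasting diuretics to hypokalemia. Marked renal impairment is allowed. Some patients can therefore be expected to enter with abnormal potassium or already taking potassium. Taken literally, the definition treats them as follows:

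- A patient who continues an unchanged home supplement meets the supplement component in either group.
- A patient who enters at, say, 3.2 mmol/L and is still low at the next sample, or is given potassium, is an event in either group.
- A patient who enters at, say, 5.2 mmol/L and is still above 5.0 at the next sample is an event, although section 3.3.4 means that spironolactone is not given at that level. Such an event cannot be a drug effect.

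Events of this kind add the same expected share to both groups and pull the risk ratio towards 1. There are 40 patients per group, no stratification by potassium is stated in 3.1, and 3.6 plans no adjustment. A chance difference in entry status could therefore pass for benefit or harm. The missing rule concerns a primary end-point, so it could otherwise be settled after results are known.

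**Working it through.** **No figure to reproduce.** Section 3.1 gives four groups of 20, hence 2 × 20 = 40 v 40 for the spironolactone comparison. The documents give no event rate, target difference or power for it.

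**Inputs from the documents.** 40 v 40 (3.1); Fisher's exact test, two-sided 0.05 (3.6).

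**Assumed inputs.** New-event risk is 45% (discharge spironolactone) v 15% (upfront) in patients not in an event state at entry. A share q of patients are entry cases, with q from 0 to 40%.

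**Step 1: literal reading, every entry case an event in both groups.** Observed rate = q + (1 − q) × risk. At q = 20%:

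- Control: 0.20 + 0.80 × 0.45 = 0.56.
- Upfront: 0.20 + 0.80 × 0.15 = 0.32.
- The difference shrinks from 30 to 24 points, and the risk ratio moves from 0.15/0.45 = 0.33 to 0.32/0.56 = 0.57.

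**Step 2: power by exact enumeration.** The anchored column keeps all 40 v 40 and counts new events only, so its rates are (1 − q) × risk (36% v 12% at q = 20%). The at-risk column drops entry cases.

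| q | Literal rates | Literal power | Anchored, all randomized | At-risk only (n per group) |
|---|---|---|---|---|
| 0% | 45% v 15% | 79% | 79% | 79% (40) |
| 20% | 56% v 32% | 51% | 65% | 69% (32) |
| 30% | 61.5% v 40.5% | 40% | 56% | 61% (28) |
| 40% | 67% v 49% | 30% | 47% | 53% (24) |

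**Step 3: other assumed risks at q = 20%.** Literal v at-risk power is 37% v 53% for 40%/15%, 52% v 75% for 40%/10%, and 24% v 41% for 30%/10%. The direction does not depend on the pair chosen.

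**Step 4: relax the assumption that every entry case counts.** Keep entry cases at 100% events in control, but let spironolactone resolve some. At 45% v 15% and q = 20%:

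- 80% remain events with spironolactone: upfront rate 0.20 × 0.80 + 0.80 × 0.15 = 0.28. Literal power is 66%, against 69% at-risk and 65% anchored.
- 60% remain: upfront rate 0.20 × 0.60 + 0.12 = 0.24. Literal power is 79%, against the same 69% and 65%.

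At q = 30% the literal figures are 62% and 81%, against 61% at-risk. The loss in Step 2 thus depends on spironolactone having no effect in entry cases.

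**Step 5: chance imbalance.** By exact binomial enumeration, the two groups differ by at least 4 of 40 entry cases (10 points) in 33% of trials at q = 20% and 42% at q = 40%.

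**The case against.** The strongest reply is that the plan never says pre-existing cases count. It uses the word incidence and a window after randomization, and needing a supplement is not obviously the same as continuing a home prescription. This stands: the defect is a missing rule, and the literal count is one reading of an ambiguous sentence.

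A reader might go further and infer that entry cases are fixed as events before spironolactone can act. The documents do not support that in general. It is strictly true only of an unchanged supplement, and only if continuation counts as need. A high entry value may fall by the next sample, since both Arm 1 strategies give loop diuretics, and a low one may recover. Section 3.5.2 does not say whether the randomization sample itself counts. Section 3.2.2 also excludes MRA use outside the protocol, which on a plain reading removes one cause of high potassium at entry.

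A reader might also infer that Hypothesis 3 can concern only new events. It names the need for supplementation as well, and a patient who enters low or supplemented can benefit by needing less. An end-point covering all randomized patients is a defensible estimand, and dropping entry cases from the primary analysis would be a different one. It would also leave the composite without a clear denominator, since a patient entering low is still at risk of hyperkalemia.

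Finally, baseline imbalance is ordinary at this size and can be handled by adjustment. That is true, but 3.6 plans none.

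**Conclusion.** The point holds as a missing baseline rule on a primary end-point. The textual gap is clear: the thresholds are absolute, eligibility has no potassium or supplement criterion, and the renal end-points show that the plan does anchor to baseline elsewhere.

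The importance is much less certain. The documents give neither the prevalence of entry cases nor any event rates. In the illustrative case of 45% v 15% with 20% entry cases all counted in both groups, power falls from 79% to 51%. If spironolactone resolves a fifth of those cases the loss relative to the alternatives nearly vanishes, and if it resolves two fifths the present wording does better. Randomization rules out reading this as systematic bias: the expected contribution is equal in both groups, and what remains is dilution and chance imbalance. The change is worth making because it is cheap and removes a choice that could otherwise be made after seeing the data.

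**What to change.** In section 3.5.2, anchor events to baseline as 3.5.3 does for renal function:

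- Count potassium supplements only if newly started or increased after randomization.
- Count potassium <3.5 or >5.0 mmol/L only as a crossing after randomization from a baseline not already in that state. State that the randomization sample is the baseline and not an event sample.
- Keep all randomized patients in the primary denominator.

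In section 3.6, analyse with stratification or adjustment for baseline potassium and baseline supplement use. Report the present wording in all randomized patients, and the at-risk-only subset, as sensitivity analyses.

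The cost is wording only, since 3.4 already collects baseline electrolytes and current therapy. There are three downsides. Fewer events are counted. Benefit in patients who enter low or supplemented is seen only in the sensitivity analysis, and if that benefit is large the anchored count has less power than the present one (65% v 79% in the 60% case above). A patient who enters low without a supplement and is then started on one still counts, so the 65%, which assumes that no entry case counts, is the favourable end; adjustment for baseline potassium addresses this in part.

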3.5.3. Secondary end-points

- Relative plasma NT-proBNP change (%) after 72 h compared to admission
- Worsening renal function defined as a >0.3 mg/dL increase in serum creatinine or a >20% decrease in estimated glomerular filtration rate by the CKD-EPI formula compared to baseline at any time point before 72 h
- Persistent renal impairment, defined as persistently elevated serum creatinine levels >0.3 mg/dL or a >20% decrease in estimated glomerular filtration rate by the CKD-EPI formula compared to baseline at the moment of outpatient follow-up 2-6 weeks after hospital discharge.
- Peak plasma aldosterone concentration (ng/L) after 72 h
- Peak plasma renin activity (ng/mL/h) after 72 h

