3.2.2. Exclusion criteria

- History of a cardiac transplantation and/or ventricular assist device
- Concurrent diagnosis of an acute coronary syndrome defined as typical chest pain and/or electrocardiographic changes in addition to a troponine rise >99th percentile
- Systolic blood pressure <90 mmHg or mean arterial pressure <65 mmHg at the moment of admission
- Use of intravenous inotropes, vasopressors or nitroprusside at any time point during the study
- A baseline estimated glomerular filtration rate <15 mL/min/1.73m² according to the Chronic Kidney Disease Epidemiology Collaboration (CKD-EPI) formula
- Use of renal replacement therapy or ultrafiltration before study inclusion
- Treatment with acetazolamide during the previous month
- Treatment with ≥2 mg bumetanide or an equivalent dose of loop diuretics during the index hospitalization before randomization
- Use of diuretics or MRA not specified by the protocol
- Exposure to nephrotoxic agents (i.e. contrast dye) anticipated within 3 days

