3.3. Interventions (See Addendum 1 for therapy schedules)

3.3.1. Arm 1, control group: High-dose loop diuretics

- At the moment of randomization the patient receives an intravenous bolus of loop diuretics at a dose equal to the double of his normal daily oral dose (e.g. a patient who takes 1x1 mg bumetanide will receive 2x1x1 mg = 2mg; or a patient who takes 2x1 mg bumetanide will receive 2x2x1 mg = 4mg).
- The next three days, the patient will receive the same dose equally divided between two administrations at 10u00 and 16u00 provided that the treating physician has concluded during the morning rounds that the patient is still volume overloaded.
- If diuresis since administration of the previous dose of loop diuretics is <1,500 mL and the patient is still volume overload, subsequent bolus doses are doubled.
- If after doubling of the dose, the patient is considered therapy-refractory. The treating physician is recommended to add chlorthalidone 50mg once daily and consider ultrafiltration or renal replacement therapy after which results of the patient will be censored.
- Switch to treatment at the discretion of the treating physician if any of the following criteria is fulfilled
 - After 3 days
 - The patient had no longer clinical signs or symptoms of congestion
 - Doubling of the serum creatinine value

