3.5.4. Other pre-specified outcome measures

- Total urinary sodium excretion (mmol) after 48 h and 72 h
- Total urine output after 24 h, 48 h and 72 h
- Change in VAS score for dyspnea at 24 h, 48 h and 72 h
- Change in 4-point Likert scale for edema at 24 h, 48 h and 72 h
- Body weight change upon hospital discharge compared to admission
- Incidence of therapy-refractory congestion defined as the need for combinational diuretic therapy with chlorthalidone, bail-out ultrafiltration or renal replacement therapy

- Incidence of all-cause mortality and readmissions after 1 year

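### Persistent renal impairment at 2-6 weeks does not count renal replacement therapy as an event, and the censoring rule can remove such patients from the end-point

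*Combined protocol and SAP*

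**What the plan says.** Section 3.5.3 gives the end-point two alternative laboratory criteria and nothing else: "Persistent renal impairment, defined as persistently elevated serum creatinine levels >0.3 mg/dL or a >20% decrease in estimated glomerular filtration rate by the CKD-EPI formula". Both are judged once only, and the timing is fixed in these words: "compared to baseline at the moment of outpatient follow-up 2-6 weeks after hospital discharge". Section 3.4 shows where the value comes from: "At an outpatient follow-up appointment 2-6 weeks after hospital discharge, a final blood sample with hematocrit" and further analytes, among them creatinine.

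The treatment schedules foresee RRT. Once a patient is judged therapy-refractory, section 3.3.1 advises the physician to add chlorthalidone and "consider ultrafiltration or renal replacement therapy after which results of the patient will be censored". Section 3.3.2 has the same sentence for the acetazolamide group. Section 3.2.2 excludes "Use of renal replacement therapy or ultrafiltration before study inclusion", so any RRT at the follow-up visit is new.

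RRT and death are counted elsewhere. Section 3.5.4 includes "bail-out ultrafiltration or renal replacement therapy" in its definition of therapy-refractory congestion and lists one-year mortality as a separate outcome. On collection, section 3.4 says: "All-cause mortality and hospital readmissions will be collected prospectively for the study cohort". Section 3.6 names the tests but gives no analysis set and no rule for death, missed visits or RRT.

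**The concern.** Starting RRT is the clearest sign of renal failure that the protocol foresees, yet it is not part of the only creatinine- or eGFR-based end-point after 72 h. Two routes lead away from counting it.

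- **Rescue RRT in the treatment phase.** The patient's later results are censored. The natural reading for a yes/no outcome at one visit is that the patient drops out. Exclusion then depends on the very condition being measured, so it is informative.
- **RRT started later or for another reason.** The censoring rule does not reach it. The patient is scored on a creatinine that dialysis has lowered, and may fall short of both criteria.

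Either route pulls the rate down in the group with more RRT. Renal safety is part of the trial's case: Hypothesis 1 in section 2 names worsening renal function among the adverse events that the acetazolamide combination may reduce. Deaths before the visit raise a further, separate question, because these patients have no value and the plan states no denominator.

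**Working it through.** **No plan figure to reproduce.** The documents give no expected rate, effect size, power or dropout for this end-point, and no frequency of RRT or early death. The only design input is section 3.1: four groups of 20, so 2 × 20 = 40 v 40 for each factor. Every patient is in one of the two Arm 1 groups, so the censoring sentence can apply to all 80.

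**How the text treats each kind of patient**

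| Patient | Treatment under the plan |
|---|---|
| Attends, no RRT | Scored on creatinine or eGFR |
| Rescue ultrafiltration or RRT in the treatment phase | Later results censored; the end-points covered are not named |
| RRT started later, ongoing at the visit | No rule; scored on the sample as drawn |
| Dead before the visit | No sample; no rule |
| Alive, visit missed | No sample; no rule |

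**Illustration (all counts assumed).** Let *e* be the impaired attenders in each group, *r* the further patients in a group who are on RRT at the visit, and *n* = 40. There are three possible scorings:

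- dropped: *e*/(*n* − *r*)
- scored not impaired: *e*/*n*
- counted as events: (*e* + *r*)/*n*

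| *e* | *r*, group A v B | Dropped | Scored not impaired | Counted | Fisher p if counted |
|---|---|---|---|---|---|
| 8 | 2 v 0 | 8/38 = 21.1% v 8/40 = 20.0% | 20.0% v 20.0% | 10/40 = 25.0% v 8/40 = 20.0% | 0.79 |
| 8 | 4 v 1 | 8/36 = 22.2% v 8/39 = 20.5% | 20.0% v 20.0% | 12/40 = 30.0% v 9/40 = 22.5% | 0.61 |
| 8 | 4 v 0 | 8/36 = 22.2% v 8/40 = 20.0% | 20.0% v 20.0% | 12/40 = 30.0% v 8/40 = 20.0% | 0.44 |
| 8 | 6 v 0 | 8/34 = 23.5% v 8/40 = 20.0% | 20.0% v 20.0% | 14/40 = 35.0% v 8/40 = 20.0% | 0.21 |
| 4 | 6 v 0 | 4/34 = 11.8% v 4/40 = 10.0% | 10.0% v 10.0% | 10/40 = 25.0% v 4/40 = 10.0% | 0.14 |

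In the 4 v 1 row, the difference is 22.2 − 20.5 = 1.7 points if these patients are dropped, 0 if they are scored not impaired, and 30.0 − 22.5 = 7.5 points if they are counted. With 2 v 0, the three differences are 1.1, 0 and 5.0 points. Because *e* is equal in the two groups, an equal split of RRT patients gives a difference of 0 under every scoring.

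**The case against.** The strongest reply is that the plan has a rule for the RRT it foresees. A reader of section 3.5.3 alone might infer that a dialysed patient is scored as recovered. The documents do not support that in general. After rescue RRT the results are censored, so the patient is removed rather than called unimpaired. Misclassification remains possible only for RRT outside that rule, and only if creatinine has fallen far enough: a dialysed patient who still meets either criterion against baseline counts as written. Nor is a raised baseline creatinine universal, since worsening renal function is one of three alternative entry criteria in section 3.2.1. This part of the reply stands. It changes the main mechanism from misclassification to informative exclusion, which is still a bias.

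Three other strong readings also fail.

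- **Death as a renal-safety outcome.** Death in heart failure need not be renal. It is a competing event, and the plan collects and reports it separately. Leaving it out of a renal definition is legitimate if it is shown alongside.
- **An attenders-only analysis set.** The plan states no such set. It follows only from where the sample is drawn; the defect is that no denominator is given.
- **A changed conclusion.** None of the illustrative splits reaches p<0.05, even 6 v 0.

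It can also be said that RRT is reported under therapy-refractory congestion. That covers bail-out use for congestion. It does not show renal status at 2-6 weeks.

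**Conclusion.** The concern holds in limited form. Two stated rules, a laboratory-only definition and censoring after rescue, together allow patients with the worst renal course to leave a renal end-point. A gap remains for RRT started outside the rescue rule. Death and missed visits are unaddressed, but death is a competing event and does not carry the point.

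The size depends wholly on how many patients are on RRT at the visit and how unevenly they fall between groups, and the documents give neither. With none, there is no effect. With an assumed imbalance of 2 to 6 patients in 40, the between-group difference is 5 to 15 points if they count and 0 to about 4 points if they do not. At this sample size that shifts the estimate, not a significance decision. The point is confined to this secondary end-point; neither primary end-point depends on the 2-6 week visit. It is worth correcting because the change is small.

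**What to change.** - In section 3.5.3, count RRT started after randomization and ongoing at the 2-6 week visit as meeting the end-point, alongside the creatinine and eGFR criteria.
- State that the censoring wording in sections 3.3.1 and 3.3.2 does not remove these patients from this end-point.
- Add RRT status at the outpatient visit to section 3.4, which does not list it now.
- Report by group, next to the end-point, the number randomized, the deaths before the visit and the missed visits. Give a composite with death only as a sensitivity analysis, since it answers a different question.

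The cost is a few sentences and one data field. The downside is that RRT begun mainly for congestion would also count as renal impairment, so the laboratory and RRT components should be shown separately.

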3.1. Study design

Randomized clinical trial with factorial 2x2 design, 2 treatment arms, and 4 groups (n=20 each):

- Arm 1: Acetazolamide + low-dose loop diuretics versus high-dose loop diuretics (=standard of care)
 - ➔ Triple blinded to treatment allocation (patient, treating physician and investigator blinded)
- Arm 2: Upfront versus discharge spironolactone
 - ➔ Treating physician and investigator blinded to treatment allocation. Patient not blinded to treatment allocation because no matching placebo will be provided due to logistic constraints.

Consecutive patients, presenting with ADHF at different Belgian hospitals will be screened by staff members, cardiology fellows, a study nurse and the cardiology Ph.D. fellows. All those people will be able to login via the website www.hartcentrumlimburg.be, where they can print the case report form and informed consent of the study and will receive the randomization number by a computer algorithm with blocks of 4.

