3.6. Statistical analysis

Continuous variables will be expressed as mean \pm standard deviation when normally distributed and as median (interquartile range) in case of a non-normal distribution. Normality will be assessed by the Shapiro-Wilk statistic. The independent-samples Student's *t*-test and Mann-Whitney *U* test will be used as indicated to compare between groups. Categorical variables will be expressed as percentages and compared using Fisher's exact test or Pearson's χ^2 -test in case of a non-binary response. Statistical significance will always be set at a 2-tailed probability level of <0.05 . All statistics will be performed using IBM SPSS® (Chicago, Illinois, USA) (version 22.0 for Mac).

4. Potential adverse events

- Metabolic acidosis is the only agent-specific adverse event that might be expected from treatment with acetazolamide. Serum bicarbonate is monitored daily. If serum bicarbonate <22 meq/L, substitution with oral NaHCO_3 will be provided.
- Hyperkalemia might be expected as a potential adverse event of spironolactone, but this medication will be withheld when serum potassium levels are >5.0 mmol/L and serum potassium levels are monitored daily throughout the study.

5. References

- american heart association. *Circulation*. 2013;127:e6-e245
2. Effect of enalapril on survival in patients with reduced left ventricular ejection fractions and congestive heart failure. The solvd investigators. *The New England journal of medicine*. 1991;325:293-302

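### Peak aldosterone and peak renin activity should be tied to the acetazolamide hypothesis and analysed with the randomized spironolactone factor in the model

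*Combined protocol and SAP*

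**What the plan says.** Section 3.1 describes a "Randomized clinical trial with factorial 2x2 design, 2 treatment arms, and 4 groups (n=20 each"), so each factor compares 40 patients with 40. Allocation is by number: the enrolling staff "will receive the randomization number by a computer algorithm with blocks of 4".

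Sections 3.5.1 and 3.5.2 give each arm its own primary end-point. Section 3.5.3 is one list for the whole trial. It includes "Peak plasma aldosterone concentration (ng/L) after 72 h" and "Peak plasma renin activity (ng/mL/h) after 72 h" and names no arm for either. Under section 3.4 both hormones are sampled at baseline and on days 1 to 3.

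In section 2, hypothesis 2 says that acetazolamide with low-dose loop diuretics "leads to less pronounced neurohumoral activation compared to treatment with high-dose loop diuretics in ADHF patients". Hypothesis 3, on spironolactone, is about safety and potassium and makes no prediction for renin or aldosterone.

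Under section 3.3.4 the upfront spironolactone group is treated from the start: "This group will receive oral spironolactone 25 mg immediately after randomization", then daily if potassium allows. Under section 3.3.3 the comparator gets neither active drug nor placebo until discharge, and section 3.2.2 excludes off-protocol use of this drug class.

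For continuous variables section 3.6 says: "The independent-samples Student's *t*-test and Mann-Whitney *U* test will be used as indicated to compare between groups". It provides no term for the other randomized factor and no interaction test.

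**The concern.** Two things are left open for the end-points that correspond to hypothesis 2.

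The first is which comparison they serve. Read literally, section 3.5.3 applies them to both arms. Spironolactone blocks the receptor on which aldosterone acts, so a circulating aldosterone level need not mean the same thing with and without the drug. The plan does not say how to read the markers in Arm 2.

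The second is the error term in Arm 1. Half of each Arm 1 group is on spironolactone. If that drug moves the markers, a two-sample test counts the movement as unexplained patient-to-patient variation, although it comes from a randomized factor that is known for every patient. What is at stake is some power for hypothesis 2 and the wording of any Arm 2 result. The primary end-points are not affected.

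**Working it through.** **Inputs from the documents.** Four groups of 20, so N = 4 × 20 = 80; 2 × 20 = 40 on upfront spironolactone; 40 v 40 for each factor; two-sided 0.05. The plan states no power, effect size or SD for these markers, so there is no figure of its own to reproduce.

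**Assumptions.** Spironolactone shifts the marker by s within-group SDs, with s from 0 to 1.5. Group sizes are equal and the two factors do not interact. The reference Arm 1 effect is the one with 80% power when s = 0:

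d = √(2/40) × (1.960 + 0.842) = 0.2236 × 2.802 = 0.626 SD.

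**Step 1, Arm 1 without the spironolactone factor.** With half of each group shifted by s, the variance within an Arm 1 group is 1 + s²/4. Approximate power is Φ(d / [0.2236 × √(1 + s²/4)] − 1.960). For s = 1: √1.25 = 1.118, 0.626 / (0.2236 × 1.118) = 2.506, and Φ(0.546) = 70.7%.

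| Shift s (SD) | Variance multiplier | Arm 1 power, unadjusted |
|---|---|---|
| 0 | 1.000 | 80.0% |
| 0.25 | 1.016 | 79.4% |
| 0.5 | 1.063 | 77.6% |
| 0.75 | 1.141 | 74.6% |
| 1.0 | 1.250 | 70.7% |
| 1.5 | 1.563 | 61.1% |

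**Step 2, simulation check** (20,000 trials of 4 × 20 per setting; t-test against an additive two-factor model).

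| s | Power, t-test | Power, two-factor | Type I error, t-test | Type I error, two-factor |
|---|---|---|---|---|
| 0 | 79.4% | 79.4% | 5.1% | 5.1% |
| 0.5 | 77.0% | 79.0% | 4.3% | 4.9% |
| 1.0 | 71.6% | 79.1% | 2.8% | 4.8% |
| 1.5 | 61.5% | 78.8% | 1.3% | 4.7% |

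The mean Arm 1 estimate was 0.626 to 0.628 throughout, so there is no bias. Its true spread across trials also stayed at about 0.22. The damage is to the estimated standard error, which is too large and makes the test conservative. The two-factor model removes this.

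**Step 3, the same shift on a ratio scale.** If the SD of the log peak is 0.6 to 0.8 (assumed), a ratio f corresponds to s = ln(f)/SD.

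| Ratio f | s | Variance inflation s²/4 | Arm 1 power |
|---|---|---|---|
| 1.3 | 0.33–0.44 | 3–5% | 78–79% |
| 1.5 | 0.51–0.68 | 6–11% | 76–78% |
| 2 | 0.87–1.16 | 19–33% | 68–73% |

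**Step 4, Arm 2.** The chance that a real shift s reaches significance at 40 v 40 is about Φ(s/0.2236 − 1.960): 20% at 0.25, 61% at 0.5, 92% at 0.75 and 99% at 1.0. This is power to detect a drug effect on a hormone level, not a false-positive rate.

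**Step 5, limits of subgroup and interaction results.** A 20 v 20 comparison has standard error √(2/20) = 0.316, so power for d = 0.626 is Φ(0.626/0.316 − 1.960) = Φ(0.02), about 51%. The interaction contrast has standard error √(4/20) = 0.447, so 80% power needs an interaction of 2.802 × 0.447 = 1.25 SD.

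**The case against.** A reader might infer more: that spironolactone raises both hormones by itself, that a higher peak in Arm 2 therefore shows the drug working, and that the trial is set to report this wrongly as harm. The documents do not support that reading. No section says that spironolactone raises either marker; the only mechanism given, in section 1, is less distal sodium reabsorption and less aldosterone breakthrough. Section 3.5.3 names measured quantities and does not label them neurohumoral activation. That term belongs to hypothesis 2. The remark in section 1 that activation of the renin axis is detrimental concerns loop diuretics. No favourable direction is set for Arm 2 and tests are two-sided, so a wrong conclusion would need an interpretation that the plan does not prescribe.

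It can also be said that the Arm 1 loss is small over much of the assumed range, about 2 points at 0.5 SD, on secondary end-points with no stated power target. The figures model a t-test, whereas section 3.6 may lead to a Mann-Whitney test. Leaving out the other factor is a general feature of section 3.6 and not special to these two markers.

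All of this stands, and it limits the point to a clarification with a modest gain in power. It does not remove the gap: the plan neither ties the markers to one comparison nor says how to read them in the other, and it sets aside a randomized factor that it already holds.

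**Conclusion.** The point holds as a low-cost improvement. The documents establish that the two markers are assigned to no arm, that only the acetazolamide hypothesis concerns neurohumoral activation, that 40 of 80 patients are randomized to spironolactone over the measurement window, and that the planned tests ignore this.

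The size depends on an assumed shift. The loss of Arm 1 power is minor up to about 0.5 SD (80% to about 78%) and material from about 1 SD (about 71%; 61% at 1.5 SD). Absent an interaction, Arm 1 has no bias and no excess of false positives. If spironolactone has no effect on the markers, nothing is lost in Arm 1. In Arm 2 the defect is a missing rule of interpretation; a misleading result there is possible but does not follow from the text.

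**What to change.** In section 3.5.3, state that peak aldosterone and peak renin activity test hypothesis 2, in the acetazolamide comparison, and are reported descriptively for the spironolactone comparison.

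In section 3.6, state that both markers are analysed in a linear model with the two randomized factors, on the log scale if skewed, and that the interaction is checked. Given the 1.25 SD needed for 80% power, a non-significant interaction should not be taken as proof that there is none. Results shown separately with and without spironolactone (20 v 20) should be supportive only.

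The cost is one model term, which is one degree of freedom, and no confirmatory Arm 2 claim on these markers. No extra patients or samples are needed, and treatment is unchanged. In the simulation the two-factor model kept Arm 1 power at about 79% for every shift tested.
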